#### **4.3 Safety evaluation endpoints and other secondary endpoints**

Adverse events shall be determined according to the definition in the code for the quality management of adverse events of medical devices. The following types of adverse events should be recorded and calculated in the hospital history and CRF. According to the CRF table, the occurrence time, starting and ending time, intervention measures and treatment results should be filled in when recording. The severity should be referred to the previous literature and CTCAE 5.0 standard.

### **5 Purpose and overall design**

#### **5.1 Purpose**

The purpose of this study is to explore whether the AI-assisted system(EndoAngel)can promote the operation training of beginners' colonoscopy.

#### **5.2 Overall design**

This is a prospective, muti-center, randomized controlled trial study.

### **6 Study process**

#### **6.1 Summary of Study Process**

- If the patient meets the inclusion criteria, the patient is invited to participate in the study and then the informed consent procedure for the clinical trial is applied.
- Assess patients' eligibility based on the inclusion/exclusion criteria.
- If the patient meets the inclusion/exclusion criteria, information prior to colonoscopy

will be collected

- If the patient is enrolled, he will be randomized
- colonoscopy is performed after informed consent. Any intraoperative adverse events are recorded on the CRF for submission and subsequent analysis.
- Follow-up will be performed from the postoperative to the study completion, as detailed in the time and event table.

## 6.2 Enrollment

Only after patients signed the informed consent, can the research-related procedures be conducted.

### 6.2.1 Informed Consent

According to the Helsinki Declaration, patients are not allowed to participate in the study without adequate informed consent. The principal investigator is responsible for ensuring that no patient was enrolled in the study without adequate informed consent. Failure to obtain informed consent and failure to document this process is considered a violation of the Helsinki Declaration and the study protocol.

All informed consent documents (ICDs) must be approved by ethics. Patient's informed consent requires documentary record on the informed consent by himself in his primary language.

The investigator or trained designated person performs a preliminary screening to determine if the patient generally meets the eligibility criteria for the study. If yes, the investigator or trained designee should recommend the patient to participate in the study. If the patient agrees to participate, they will need to sign an informed consent document.

The investigator or trained designated person should confirm that the subject understands the following points in the study:

- The purpose of research,
- Potential risks or adverse events,
- Potential risks or adverse events directly related to participating the research,
- The likelihood of failure,
- Research requirements include follow-up visits,
- All rights of the subject as a participant in the clinical study.

After explaining the purpose of the study, the investigator or trained designee should answer any questions from the subject. If the subject agrees to participate, his or her wishes must be recorded by signing and dated on the EC-approved ICF, and the document should be signed and dated by the patient receiving the informed consent.

After successful completion of the informed consent process, the investigator or trained designated person will assess the eligibility of patients based on the protocol.

### **6.2.2 Patient Selection**

All endoscopists and patients who needed colonoscopy agreed to use their results for correlation analysis, were screened based on the inclusion/exclusion criteria. Patients who passed the screening were enrolled and recorded in the subject screening and enrollment tables. There is no bias in the choice of the enrolled subjects. The date of screening, the results (enrolled or not), and the primary reason for not selecting subjects (such as not meeting inclusion criteria, or not interested in participating in the study) will be recorded.

After the patients are enrolled, the research center should complete the preoperative study data collection.

It is desirable to be able to collect complete data for all enrolled patients, without who withdrawal from the study.

### **6.2.3 Subject identification number**

Each subject is numbered after obtaining informed consent.

The colonoscopist number starts with EAE as a fixed number and starts with 0001 according to the time of obtaining the informed consent. For example, subject No. 1 signed the informed consent was EAE0001, followed by subject No. 2, EAE0002.

The colonoscopy patients were numbered starting with EA as a fixed number and starting with 0001 according to the time of obtaining the informed consent. For example, the number of the first subject to sign the informed consent in Southern Medical was EA0001, followed by the second subject EA0002.

Once the subject identification number is assigned, the number is not reusable.

## **6.3 Treatment Description**

This section applies to individuals who have signed an approved informed consent and

have been identified as eligible to participate in this study on the basis of the inclusion and exclusion criteria. This section introduces the preoperative, surgical and postoperative management of subjects in detail.

### **6.3.1 Patient Screening Assessments**

- 1) History
- 2) Physical examination
- 3) Hematuria pregnancy test (if required)

### **6.3.2 Pre-Procedure Managements**

- 1) Fasting for 6 hours and water deprivation for 2 hours before examination
- 2) Routine intestinal preparation.
- 3) Psychological counseling.
- 4) Performing routine anesthesia for painless colonoscopy patients.

### **6.3.3 Intraoperative Managements**

- 1) Patient position: prone position with appropriate restraint.
- 2) Insertion route: according to the actual situation of the subject, usually through the anus
- 3) Patients in the control group received colonoscopy without AI assistance, and patients in the experimental group received colonoscopy with AI assistance. The advanced physician carries on the colonoscopy examination under the teacher's guidance.
- 4) After the examination, the teacher scored the colonoscopy according to the ACE scoring scale.

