Study Process:	
1. Subjects meeting all inclusion criteria and those failing all exclusion criteria were included in the study before colonoscopy;
 
2. Include qualified novice doctors for colonoscopy training
 
3. Patients who met the requirements were enrolled and randomly assigned as follows
 
The experimental group: received painless colonoscopy training with the assistance of the artificial intelligence assistant system, which could prompt abnormal lesions and real-time withdrawal speed, and feedback the overspeed percentage.
 
Control group: routine painless enteroscopy training, no special tips.
 
4. After colonoscopy, the teacher scored the colonoscopy using ACE scoring scale

Security	Safety incidents shall be evaluated and reported according to the quality management measures for clinical trials of medical devices

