Based on the above rich foundation of preliminary work and the huge demand in the field of colonoscopy training, we intend to train beginners in colonoscopy operation by comparing the cases of EndolAngel assistance and no EndolAngel assistance. To explore whether AI can promote the training of colonoscopy for beginners.

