## **4 Endpoints**

### **4.1 Primary Endpoint**

- 1) CUSUM learning curve for colonoscopy (ACE scoring scale)
- 2) Average test score difference before and after training

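### ACE is scored with AI on in one arm and off in the other, so the ACE comparison cannot separate what trainees learned from live assistance

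*Combined protocol and SAP*

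**What the plan says.** The aim concerns training. Section 2 puts it as "To explore whether AI can promote the training of colonoscopy for beginners", and section 5.1 asks whether the system "can promote the operation training of beginners' colonoscopy".

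The conditions of the scored examinations are in section 6.3.3: "Patients in the control group received colonoscopy without AI assistance", and "patients in the experimental group received colonoscopy with AI assistance". The same section then says: "After the examination, the teacher scored the colonoscopy according to the ACE scoring scale". In the Summary (Study Process), the experimental group trains with a system "which could prompt abnormal lesions and real-time withdrawal speed, and feedback the overspeed percentage", while the control group gets no special tips.

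Section 4.1 names two primary endpoints. The first is a CUSUM learning curve built on ACE. The second is "Average test score difference before and after training". Section 8.3 sizes the trial on ACE alone: cognitive score from 2.5 to 2.8 (126 cases), motor score from 2.38 to 2.59 (350 cases), and 385 cases after a 10% allowance for dropout.

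Sections 3.3, 6.1 and 6.5.1 randomise before colonoscopy. Section 6.5.1 says that this allocation decides whether EndoAngel is used.

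**The concern.** A claim about training is a claim about what the trainee can do afterwards. Here, each experimental ACE score comes from an examination in which the device is giving prompts, and each control score comes from one in which it is not. The score may pick up skill that the trainee has acquired, help that the device gives at that moment, or both.

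Section 7.6 makes a live effect likely on the sponsor's own account. It treats EndoAngel's benefit to examination quality as already proven and expects that assisted patients may have better examinations. An ACE difference could then appear with no extra learning at all. The CUSUM format does not remove the problem, because a steady lift in case scores would also improve an assisted trainee's curve. Section 8.2 gives no CUSUM target and no between-arm ACE analysis that would separate the two.

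At stake is a headline that AI improves training, resting on a gain that might not persist with the display off.

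**Working it through.** **1. The plan's own figure.** 350 × 1.10 = 385, as stated. (Dividing by 0.90 would give 389; the gap is immaterial here.)

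**2. What the ACE contrast contains, under each reading of the allocation.**

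| Reading | Where it comes from | What the ACE difference contains |
|---|---|---|
| Patients randomised within trainee | Summary (Study Process), 3.3, 6.1, 6.5.1 | Trainees work in both arms, so learning is shared; essentially live assistance |
| One allocation per trainee | Summary wording about a group trained with AI | Learning plus live assistance, mixed |

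Neither reading isolates learning. The text available describes no ACE assessment with both arms under the same AI condition.

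**3. Illustration of size.** Section 8.3 gives no SD, alpha or power. Assume two-sided alpha 0.05, 1:1 allocation, the stated case numbers as totals, and independent cases. The implied SD is

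SD = δ × √(N/4) / (1.96 + z_power), with z_power = 0.842 (80%) or 1.282 (90%).

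- Motor, δ = 2.59 − 2.38 = 0.21, N = 350: 0.21 × 9.354 / 2.802 = 0.70 at 80% power; / 3.242 = 0.61 at 90%.
- Cognitive, δ = 2.8 − 2.5 = 0.30, N = 126: 0.30 × 5.612 / 2.802 = 0.60 at 80%; / 3.242 = 0.52 at 90%.

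Now assume that half of each planned difference is learning (0.105 and 0.15), and that ACE is compared on 350 cases with AI off in both arms. Power = Φ(δ / (SD × √(4/350)) − 1.96), with √(4/350) = 0.1069.

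| Score | Learning part | SD | δ/SE | Power |
|---|---|---|---|---|
| Motor | 0.105 | 0.70 | 1.40 | 29% |
| Motor | 0.105 | 0.61 | 1.61 | 36% |
| Cognitive | 0.15 | 0.60 | 2.34 | 65% |
| Cognitive | 0.15 | 0.52 | 2.70 | 77% |

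Under the planned scoring, by contrast, a total motor difference of 0.21 is equally likely to reach significance whether it splits as 0 learning + 0.21 live, 0.105 + 0.105, or 0.21 + 0. The test sees only the sum.

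These figures ignore clustering by trainee; the documents give neither the number of trainees nor an intraclass correlation. The half split is not an estimate.

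**The case against.** The strongest reply is that ACE is not the whole trial. The before/after test is also a primary endpoint and is a training outcome by nature. If it is taken without AI, it compares like with like. This stands. A reader might infer that the trial cannot show any training benefit, but the documents do not support that: the limit applies to ACE and its CUSUM curve. What remains open is that the test's content, timing, AI status and analysis are not described, and that 8.3 does not size for it.

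Three further cautions also stand.

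- A reader might infer that a trainee who merely followed the prompts would score higher. The documents do not list the ACE items, and the prompts described concern lesions and withdrawal speed. Such a trainee could score higher; whether the motor score would move cannot be checked here.
- A reader might infer that a pure live effect of 0.21 would make the trial positive 80% of the time. That 80% only returns the power assumed when the SD was back-solved, so it is not evidence.
- The absence of a like-for-like ACE score can be stated only for the text available. The flow chart in 1.2 is not shown there, and 7.1 refers other evaluations to the CRF.

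It can also be said that the aim is exploratory. This softens the consequence but does not change what an ACE difference can be attributed to.

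**Conclusion.** The concern holds for the ACE comparison. As planned, a difference in ACE or in its CUSUM curve shows performance during assisted versus unassisted colonoscopy and cannot be attributed to training. With patients randomised within trainee, it is essentially a measure of live assistance; with one allocation per trainee, it mixes the two. This follows from 6.3.3 and the Summary and needs no numerical assumption.

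The documents do not fix the size of the live component. The power ranges of 29% to 36% (motor) and 65% to 77% (cognitive) depend on an assumed half split, assumed alpha, back-solved SDs and independent cases; they illustrate the problem and estimate nothing. The matter should be corrected because it bears on what the trial may conclude from its first primary endpoint.

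**What to change.** 1. In 5.1 and 8, limit the conclusion drawn from ACE and its CUSUM curve to performance during AI-assisted versus unassisted colonoscopy. This is wording only; the cost is a narrower claim.
2. In 4.1, describe the before/after test, state that it is taken without AI in both arms, and rest any training claim on it. The test belongs to the trainee, so an arm comparison is possible only if each trainee has a single allocation. Its precision would depend on the number of trainees, which the documents do not give.
3. If patients remain the randomised unit, drop the training claim.

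An optional addition, which is not cheap, is to score ACE on final assessment cases with the display off in both arms. This needs trainee-level allocation and loses much of the sample. If 70 of the 350 cases were used (assumption), power for the full motor difference of 0.21 would be Φ(0.21 / (0.70 × √(4/70)) − 1.96) = Φ(1.25 − 1.96), about 24%, or about 30% with SD 0.61, before any allowance for clustering. It should be sized properly before it is adopted.

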### **6.3.4 Post-operative Managements**

[figure not shown]
- 1) Postoperative routine nursing
- 2) The anesthetized subjects were observed until they woke up
- 3) Patients with no lesions such as polyps were followed up until they woke up and left

the endoscopic room.

- 4) Clinical information such as the examining physician, duration of examination, sedation status, whether to ileocecal reach, bowel readiness, complications, polyp characteristics (number, location, size, color, and shape), and pathological results will be collected and recorded in a Web-based data management system.
- 5) The images and video data were collected for the functional evaluation of EndoAngel, such as the withdrawal speed, the number of sliding not returned/sliding returned, real-time intestinal preparation score, polyp detection and typing, etc.

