## 1.1 Time and Event Tables

Events/visits	Screening period (d -30~-1)	The day of colonoscopy(d 0)	Follow-up(d 1-14)
Informed Consent	X		
Demographic information	X		
Urine/blood pregnancy test	X		
Medical history/surgical history	X		
physical examination	X		
Selection/exclusion criteria	X		
colonoscopy		X	
Accompanying therapy	X	X	
Accompanying medication	X	X	
Adverse events		X	X
Pathological findings			X
Research completed			X

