## 1.2 Flow chart

## 2 Introduction

Endoscopic diagnosis and treatment play an important role in the discovery and treatment of digestive tract diseases. Common endoscopic examination includes gastroscopy, colonoscopy, enteroscopy, capsule endoscopy, ultrasound gastroscopy, endoscopic retrograde cholangiopancreatography and other related techniques, which can be used in the diagnosis and follow-up of early gastric cancer, peptic ulcer, esophageal varices, precancerous lesions, intestinal polyps, intestinal adenomas, bowel cancer lesions, inflammatory bowel diseases, pancreatic diseases, biliary diseases, etc. At present, digestive endoscopy almost covers the diagnosis of most diseases of the digestive tract, and the digestive system diseases that can not be seen in the direct visual field of endoscope can also be realized by the related techniques based on ultrasound endoscopy, ERCP and other endoscopy (we call endoscopy here), so as to achieve the coverage of the whole digestive system. It can be seen that digestive endoscopy is of great significance for the diagnosis and development of digestive system diseases. At present, the demand for endoscopic examination in China is high, and the supply of endoscopic surgery in hospitals is short of supply, which puts forward high requirements for the proficiency and accuracy of operation doctors.

In recent years, deep learning has developed rapidly in the field of medicine. Andre Esteva et al. used deep neural networks (DNN) to classify skin cancer to an expert level. Our previous experiments show that deep learning has high accuracy in endoscopic quality monitoring, which can effectively standardize the operation of doctors, reduce the blind area of examination, and improve the quality of endoscopic examination. At the same time, it can also monitor the doctor's withdrawal time and improve the detection rate of adenoma. in the previous work of our group, we have successfully developed a deep learning-based enteroscopy speed monitoring, intestinal cleanliness evaluation, and in clinical trials to verify the effectiveness of artificial intelligence model in improving the quality of gastroscopy, enteroscopy.

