### **4.2 Secondary Endpoints**

- 1) Detection rate of advanced adenoma: the numerator is the number of patients diagnosed with advanced adenomas, and the denominator is the total number of patients undergoing colonoscopy, Advanced adenoma was defined as > 10mm adenoma, villous adenoma, tubular villous adenoma, high-grade intraepithelial neoplasia, and carcinoma.

- 2) Polyp Detection Rate, PDR: the numerator is the number of patients with polyps detected by colonoscopy, and the denominator is the total number of patients who underwent colonoscopy
- 3) Average number of adenomas detected per patient: the numerator is the total number of adenomas detected by colonoscopy, and the denominator is the total number of patients undergoing colonoscopy.
- 4) The detection rate of large, small and micro polyps: the numerator is the number of patients with large ( $\geq 10$  mm), small (6-9 mm) and micro-small ( $\leq 5$  mm) polyps detected by colonoscopy, and the denominator is the total number of patients receiving colonoscopy.
- 5) The average number of large, small and micro polyps detected: the numerator is the total number of large ( $\geq 10$  mm), small (6-9 mm) and micro-small ( $\leq 5$  mm) polyps detected by colonoscopy, and denominator is the total number of patients undergoing colonoscopy.
- 6) The detection rate of large, small and micro adenomas: the numerator is the number of patients with large ( $\geq 10$  mm), small (6-9 mm) and micro-small ( $\leq 5$  mm) adenomas detected by colonoscopy, and the denominator is the total number of patients receiving colonoscopy.
- 7) The average number of large, small and micro adenomas detected: the numerator is the total number of large ( $\geq 10$  mm), small (6-9 mm) and micro-small ( $\leq 5$  mm) adenomas detected by colonoscopy, and denominator is the total number of patients undergoing colonoscopy.
- 8) The detection rate of adenoma in different sites: the numerator is the number of patients with adenomas detected in the rectum, sigmoid colon, descending colon, transverse colon, ascending colon, ileocecal region and other sites during colonoscopy, and the denominator is the total number of patients receiving colonoscopy.

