### **6.5 Randomization and Blinding**

#### **6.5.1 Randomization Implementation**

Randomization is conducted according to the study protocol, and the random contents are implemented in an electronic system block-randomized manner (n = 4; experimental group/control group = 1). Randomization prior to Colonoscopy to decide whether to use EndoAngel. The researchers randomized the random results generated by the electronic system, and the generated random results were stored in the research center. The random time (accurate to minute), random person, subject number and acronym were recorded in the corresponding positions of the electronic system.

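### Section 6.3.4 ends follow-up of lesion-free patients when they leave the endoscopy room, while Table 1.1 marks adverse events for days 1 to 14 without a lesion condition; the two need reconciling so that adverse-event capture cannot depend on lesion detection

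*Combined protocol and SAP*

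**What the plan says.** Section 6.3.4 (Post-operative Managements), item 3, deals separately with patients in whom nothing was found: "Patients with no lesions such as polyps were followed up until they woke up and left" the endoscopy room. Item 2 of the same list already covers observation of anaesthetised subjects until they wake.

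The time and event table in section 1.1 has a visit column headed "Follow-up(d 1-14", that is, days 1 to 14. Its adverse-event row is marked both for the day of colonoscopy and for this column. No restriction by lesion status is given.

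Section 6.1 points to that table: "Follow-up will be performed from the postoperative to the study completion, as detailed in the time and event table". It sets no lesion condition either.

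Section 4.3, on safety endpoints, requires recording without reference to lesions: "The following types of adverse events should be recorded and calculated in the hospital history and CRF".

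On the intervention, the Summary says of the AI system in the experimental group: "which could prompt abnormal lesions and real-time withdrawal speed". The control group gets no such prompts. The Introduction credits the technology with being able to "improve the detection rate of adenoma". Polyp detection rate is a secondary endpoint in section 4.2, where "the numerator is the number of patients with polyps detected by colonoscopy".

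**The concern.** Two rules for the length of follow-up stand side by side and nothing says which governs adverse-event collection. Under the table, the window is the same for all patients. Under 6.3.4 item 3, a lesion-free patient's window closes on day 0.

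The second rule would matter for two reasons. First, delayed events in lesion-free patients would not be recorded in either arm. Section 7.3 defines an adverse event broadly, whether or not it is related to the device, so these patients are not outside the scope of safety recording. Second, whether a lesion is found is known only after randomisation, and the AI prompts act on it. If the AI arm finds more lesions, more of its patients are followed beyond day 0 and more of its delayed events are recorded, even at identical true risk. Randomisation does not protect a comparison whose observation time depends on an outcome of treatment.

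At stake is the reading of the adverse-event tabulation by arm under section 4.3. The primary endpoints (ACE/CUSUM learning curve and test-score difference) do not use days 1 to 14 and are not touched.

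**Working it through.** **Comparison of the passages**

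| Place | Window for adverse events or follow-up | Lesion condition |
|---|---|---|
| Section 1.1, table | Day 0 and days 1 to 14 | None |
| Section 6.1 | To study completion, by reference to the table | None |
| Section 4.3 | No window given | None |
| Section 6.3.4, item 3 | Until departure from the endoscopy room | Applies if no lesion is found |

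The first three are compatible with each other. The fourth is not, if it governs adverse-event collection.

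**Illustration of size.** The documents state no figure to reproduce: they give neither a lesion rate nor an adverse-event rate. The inputs are:

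- from the documents: 385 colonoscopies (section 8.3) and equal allocation, "experimental group/control group = 1" (section 6.5.1), hence 385/2 = 192.5 per arm;
- assumed: lesion found in 40% of control and 50% of AI patients;
- assumed: events on days 1 to 14 are recorded only where a lesion was found;
- assumed: lesion-free patients have delayed-event risk r in both arms, and patients with a lesion have k × r.

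*Patients without follow-up on days 1 to 14.* Control: 0.60 × 192.5 = 115.5. AI: 0.50 × 192.5 = 96.25.

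*Recorded ratio, AI to control.* (0.50 × k × r)/(0.40 × k × r) = 1.25 for every k, because only lesion patients contribute.

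*True ratio.* (0.5k + 0.5)/(0.4k + 0.6).

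*Spurious part* = recorded ratio / true ratio:

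| k | True ratio | Spurious part |
|---|---|---|
| 1 (equal risk) | 1.0/1.0 = 1.00 | 1.25 |
| 5 | 3.0/2.6 = 1.15 | 1.08 |
| 10 | 5.5/4.6 = 1.20 | 1.05 |
| All delayed events in lesion patients | 0.5/0.4 = 1.25 | 1.00 |

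*Other detection gaps, with k = 1.* 30% v 40%: 0.40/0.30 = 1.33. 50% v 60%: 0.60/0.50 = 1.20. 40% v 40%: 1.00, although 60% of delayed events would still be missed in each arm.

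*Absolute scale, with k = 1 and an assumed true delayed risk of 2%.* Expected events per arm: 0.02 × 192.5 = 3.85. Recorded, control: 0.02 × 0.40 × 192.5 = 1.54. Recorded, AI: 0.02 × 0.50 × 192.5 = 1.93. The difference is about 0.4 of an event. The loss is 2.31 events in control (3.85 − 1.54) and 1.92 in AI (3.85 − 1.93), so under-counting is larger than the spurious difference.

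All these ratios concern delayed events. Adding day-0 events, which are recorded for everyone, would dilute them.

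**The case against.** The strongest counter-argument is that 6.3.4 is a list of post-procedure care and item 3 describes recovery-room observation, not data collection. Section 6.1 sends follow-up to the table, so the table would govern and capture would not depend on detection. This reading is possible but strained. Item 2 already covers observation until waking, and item 3 adds a separate rule for lesion-free patients in the language of follow-up. At best the text is ambiguous, and three hospitals (section 8.3) could apply it differently.

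A mark in the table also need not mean every patient. The pregnancy test is marked but section 6.3.1 makes it conditional, and pathology on days 1 to 14 can apply only where tissue was taken. Neither the table nor 6.1 says in terms that every patient has adverse events collected to day 14. That weakens the contradiction. However, if the mark means only where applicable, the lesion-dependent window remains.

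The remaining objections concern size, and they stand. Biopsy and polyp removal are foreseen, so risk may be higher where a lesion is treated, which shrinks the spurious part. Section 6.6 records concomitant treatment, including treatment of adverse events, to study completion, so some delayed events might surface that way, although the table marks that item only to day 0. Both arms work under a teacher's guidance (section 6.3.3), which may narrow any detection gap.

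A reader might infer more than the documents support:

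- That adverse-event capture in this trial does depend on lesion detection. It does so only if sites apply 6.3.4 in preference to the table.
- That the AI arm will show an excess of a quarter or more. The documents give no detection gap, and such a ratio also needs equal delayed risk with and without a lesion.
- That a planned safety test is biased. Section 8.2 names no between-arm test of adverse events; what is affected is the tabulation.
- That safety is a headline aim of this trial. Safety appears in the title of the overall project. Subtopic 4 is titled as a study of effectiveness, and section 5.1 gives training as the purpose. Safety endpoints are nonetheless listed in section 4.3.

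**Conclusion.** The inconsistency is real and unreconciled. Its consequence is conditional: if sites apply 6.3.4 item 3 to adverse-event collection, delayed events in lesion-free patients are lost, and observation time depends on a post-randomisation outcome that the AI is expected to raise. The safety tabulation by arm would then be under-counted and possibly differential.

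The documents do not allow the size to be derived. At assumed lesion rates of 40% v 50%, the spurious ratio for delayed events lies between 1.00 and 1.25, provided that risk in lesion patients is at least that in lesion-free patients and that nothing is captured after a lesion-free patient leaves. Without a detection gap the ratio is 1.00 and only the under-count remains. In absolute terms few events would be involved. This is worth correcting because the correction is cheap. It does not threaten the primary analysis.

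**What to change.** Reconcile section 6.3.4 item 3 with Table 1.1 and section 6.1. Whichever adverse-event ascertainment window the sponsor keeps, state that it is the same for every randomised patient in both arms, whether or not a lesion was found. If item 3 is meant only as recovery-room observation, say so and add that it does not limit adverse-event collection.

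If a shorter window is kept for lesion-free patients, present adverse-event rates by arm only for the period observed in everyone, and report later events separately with the number of patients followed.

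The cost is protocol wording and at most one follow-up contact for lesion-free patients, which Table 1.1 already foresees. The change concerns data collection only and implies nothing about clinical care after the examination.
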